### 3. Objectives and Endpoints

Objectives	Endpoints/Assessments

Primary
 
 
To assess the safety of continued treatment with RLM for participants who previously completed the RLM-MD-03 or RLM-MD-04 study
 
	
 
No endpoints were specified for this study. Safety assessments include: AEs, clinical laboratory values, vital signs, ECGs (reported as clinically significant AEs)
 

### 4. Study Design

#### 4.1. Overall Design

Study 3071-305-020 is an open-label, multicenter, multinational safety study in participants with DG who completed the Phase 3 studies, RLM-MD-03 or RLM-MD-04, and have no ongoing AEs from either lead-in study that, in the investigator’s opinion, would preclude participation. Participants who discontinued Studies RLM-MD-03 or RLM-MD-04 for any reason are not to be enrolled into this study. Participants who roll over to this continued access study within 30 days (ie, ≤ 30 days) of completing their final visit assessments in either Study RLM-MD-03 or Study RLM-MD-04 do not need to complete baseline assessments; information from the final visit of Studies RLM-MD-03 or RLM-MD-04 will be used as the information for Visit 1 of this study (see Section 8). Visit 1 should occur in ≤ 30 days of the last visit of the lead-in study. If a participant enters this continued-access study > 30 days after last visit in either lead-in study, Visit 1 baseline assessments will be completed as shown in Section 1.3

Approximately 1000 participants may roll over from Studies RLM-MD-03 or RLM-MD-04 at approximately 700 sites with an anticipated attrition rate of approximately 20% per year. No participant replacement is planned in this continued-access, open-label study.

##### 4.1.1. Clinical Hypotheses

There is no specific clinical hypothesis related to the efficacy of treatment.

#### 4.2. Scientific Rationale for Study Design

The Phase 3 studies will provide placebo-controlled information on the safety and efficacy of RLM in the treatment of DG. This open-label continuation of treatment will provide additional information on the long-term safety of RLM. The current study, will provide sufficient long-term safety information to support the safe use of RLM as a chronic treatment of DG.

Relamorelin

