### 4.4. End of Study Definition

This study will continue until RLM becomes commercially available or the sponsor terminates development.

A participant is considered to have completed the study if he/she has completed a final visit assessment.

Relamorelin

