**9.2. Sample Size Determination**

There were no sample size calculations performed for this study.

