### 9.4. Statistical Analyses

The SAP will be developed and finalized before database lock and will describe the participant populations to be included in the analyses. This section is a summary of the planned statistical analyses:

Methodology	Description
Categorical counts	
 
• Number of participants in individual categories                             
 
○ Participants with <math>\geq 1</math> qualifying event counted once per individual category
 
 
 

Categorical descriptives	
 
• Number and percentage of participants in individual categories                             
 
○ Participants with <math>\geq 1</math> qualifying event counted once per individual category
 
 
 
• N1 if percentage denominator <math>\neq</math> number of participants in the population (standard percentage denominator)                             
 
○ N1 = participants with nonmissing baseline value
 
 
 

Continuous descriptives	
 
• N1, mean, SD, median, minimum, maximum
 
• N1 = participants with nonmissing value
 

Event descriptives	
 
• Number and percentage of events in individual categories                             
 
○ Events counted individually for each instance
 
 
 
• Percentage denominator = total number of events
 

CFB descriptives	
 
• Continuous descriptives for baseline, postbaseline, and change from baseline (CFB) values
 
• N1 = participants with nonmissing values at both baseline and the specified postbaseline analysis visit
 

Shift analyses	
 
• Number and percentage of participants in individual baseline and postbaseline categories
 
• Percentage denominator = number of participants in individual baseline categories
 
• N1 = participants with nonmissing values at both baseline and the specified postbaseline analysis visit
 

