#### 9.4.1. Safety Analyses

The safety analysis will be performed using the safety population and will be fully defined in the SAP. No endpoints were specified for this study. The safety parameters will include AEs, vital signs, clinical laboratory tests (hematology, clinical chemistry including HbA1c, urinalysis), and ECG values reported as clinically significant AEs.

Relamorelin

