### **9.5. Interim Analyses**

No interim analysis is planned.

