### **9.6. Data Monitoring Committee**

A Data Monitoring Committee was not used for this study.

Relamorelin

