**10.1.5. Posting Clinical Study Data**

All data generated in this study are the property of the sponsor. An integrated clinical and statistical report will be prepared at the completion of the study.

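### Does the claim of sufficient long-term safety information fail because no pooled analysis is scheduled before the study ends?

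*Protocol*

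**What the plan says.** Section 4.2 first assigns the placebo-controlled evidence to the Phase 3 studies and describes this continuation as giving additional long-term safety information. It then makes the stronger statement that the study "will provide sufficient long-term safety information to support the safe use of RLM as a chronic treatment of DG".

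The timing is set elsewhere:

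- Section 4.4: "This study will continue until RLM becomes commercially available or the sponsor terminates development".
- Section 9.5: "No interim analysis is planned".
- Section 10.1.5: "An integrated clinical and statistical report will be prepared at the completion of the study".
- Section 9.4: "The SAP will be developed and finalized before database lock".
- Section 9.6: "A Data Monitoring Committee was not used for this study".

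No quantity is attached to the claim. Section 9.1 has no hypothesis, Section 9.2 states "There were no sample size calculations performed for this study", and Section 9.4.1 states "No endpoints were specified for this study". Section 4.1 expects about 1000 participants to roll over, with attrition of about 20% a year and no replacement. Anyone who discontinued a lead-in study is excluded.

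**The concern.** Taken literally, the two end-of-study triggers leave the planned read-out with little to do. Under the first, the pooled adverse-event, HbA1c and laboratory tables are produced after the drug is on the market. Under the second, there is no chronic use left to support. The protocol itself fixes the absence of an interim analysis and of a monitoring committee, so the point cannot be passed to the SAP.

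The word sufficient also invites a question that the protocol does not answer: sufficient to exclude what, and with what precision? There is no comparator, and the population consists of lead-in completers, which under-represents people who could not tolerate the drug.

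If the concern held, hundreds of serious events could accrue among about 1000 participants before anyone tabulated them. The only data in this protocol beyond about 12 months of treatment would then play no part in approval, labelling or the ongoing judgement of benefit and risk.

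**Working it through.** The protocol gives no sample size, precision or exposure figure, so there is nothing of its own to reproduce. Two checks are possible: how much information the study would accrue, and whether the text prevents its use.

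**Inputs.** N is about 1000 and attrition about 20% a year (Section 4.1). In the 12-week Phase 2b study there were 23 SAEs in 289 participants on relamorelin and 8 in 104 on placebo (Section 2.2; duration from Section 4.3). Assumptions: everyone enters at time zero, attrition is constant, and Phase 2b exposure was the full 12 weeks.

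**Background SAE rate.**
- Relamorelin: 23 / (289 × 12/52) = 34.5 per 100 person-years.
- Placebo: 8 / (104 × 12/52) = 33.3 per 100 person-years.

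**Exposure.** Participants remaining = 1000 × 0.8^t. Cumulative person-years = 1000 × (1 − 0.8^t) / (−ln 0.8). Expected SAEs = 0.345 × person-years.

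| Year | Remaining | Person-years | Expected SAEs |
|---|---|---|---|
| 1 | 800 | 896 | 309 |
| 3 | 512 | 2187 | 754 |
| 5 | 328 | 3013 | 1039 |

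The SAE projection is rough. The relamorelin rate pools 10, 30 and 100 µg BID, whereas this study uses 10 µg BID only. It is carried over to selected completers. This protocol does not count the listed manifestations of gastroparesis as AEs or SAEs (Section 10.3.1), and whether Phase 2b did the same is not stated.

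**Precision for an event never seen.** Counting only those still enrolled, the one-sided 95% upper bound on risk is 1 − 0.05^(1/n): 0.37% for n = 800, 0.58% for n = 512 and 0.91% for n = 328. This looks like precision worsening with time, but it is not. The three figures bound risks over 1, 3 and 5 years, and they discard all time contributed by people who left. Dividing by the number of years already reverses the trend: 0.37, 0.19 and 0.18% per year.

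Using all person-time, the upper bound on the rate is −ln(0.05) / person-years:

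- Year 1: 2.996 / 896 = 0.33 per 100 person-years.
- Year 3: 2.996 / 2187 = 0.14 per 100 person-years.
- Year 5: 2.996 / 3013 = 0.10 per 100 person-years.

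If only 500 people entered, these bounds would double, to about 0.67, 0.27 and 0.20.

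**Does the text block use of the data?** Section 6.3 makes the study open-label and Section 9.1 gives it no hypothesis. There is no blind to protect and no type I error to spend, so Section 9.5 means only that no interim analysis is scheduled. It does not prohibit a descriptive cut. Sections 1.1 and 2.1 say the regulatory assessment concerns the Phase 3 results, which include safety studies of up to 12 months; this study offers access while that assessment proceeds. Nothing says its own report must come first.

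**Are events unobserved until the end?** No. SAEs go to the sponsor within 24 hours (Section 8.3.1), and the sponsor carries the regulatory reporting duties, including SUSARs (Section 8.3.4). Investigators review each laboratory report (Section 8.2.4). Laboratory alerts for potential liver injury go to sponsor and investigators at once (Appendix 9). Ethics committees receive status summaries at least annually (Section 10.1.1).

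**The case for a change.** The best argument for a change is that case-level reporting cannot show a drift in a group mean. Section 2.2 reports rising HbA1c that changed little after about 8 weeks. Section 4.3 describes an increase at 12 weeks with 10 µg BID that had not been seen at 4 weeks. What happens beyond a year is an open question that pooled data from this study would answer, and periodic cuts of the Section 9.4.1 tables would need no extra visits and no alpha adjustment. The near-equal Phase 2b SAE rates, 34.5 and 33.3 per 100 person-years, also show that uncontrolled counts cannot by themselves separate drug from disease.

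Part of this stands. The word sufficient has no stated basis, and no pooled summary is scheduled before the end of the study. But the lack of a comparator and the restriction to completers are inherent in a rollover extension and are stated openly; they are not errors. Scheduled annual cuts would be a reasonable addition, but they would not correct a wrong rule or figure. The sponsor can run them without the protocol saying so, and cumulative safety reporting at programme level would sit in documents not seen here. The stronger claim, that the data could not inform approval, labelling or benefit-risk, does not follow from the text.

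**Conclusion.** No change to the plan is needed. The concern correctly identifies an overstated sentence in Section 4.2, whose preceding sentence already gives the accurate description: additional safety information from an uncontrolled continuation. Rewording it would alter no analysis, population, definition or result, and the end-of-study descriptive tables are sound for the stated objective.

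The numbers do not show a shortage of information. Exposure of about 896 to 3013 person-years over 1 to 5 years gives zero-event rate bounds that tighten from about 0.33 to 0.10 per 100 person-years. This assumes 1000 participants entering together, 20% yearly attrition and a constant event rate; slower or smaller enrolment widens the bounds in proportion to the person-years lost. The conclusion on timing rests on reading Section 9.5 as an absence of schedule rather than a prohibition, which is the natural reading in an open-label study with nothing to test.

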### 4.3. Justification for Dose

A RLM dose of 10 µg SC BID will be used, which is the same as the dose in the Phase 3 program.

This dose was selected based on clinical safety and efficacy data from Study RLM-131-009, which also provided PK and PD information for the 10 µg dose.

Study RM-131-009 was a 12-week Phase 2b, randomized, double-blind, placebo-controlled, parallel-group study to evaluate the safety and efficacy of RLM in diabetic participants with moderate to severe DG. The doses included within the study were 10 µg BID, 30 µg BID, and 100 µg BID. In general, all doses tested within Study RM-131-009 appeared to demonstrate meaningful reductions in overall DG symptom scores, including vomiting episodes, with acceptable safety and tolerability. The frequency of vomiting episodes was reduced from baseline over the 12-week treatment period to a similar extent for participants who received the 3 doses of RLM tested and placebo. Based upon the observed dose response of change-from-baseline symptom scores collected daily over the course of 12 weeks using the DGSSD, the 30 µg BID and 100 µg BID doses demonstrated apparent maximal effects, while the 10 µg BID dose achieved near maximal reductions. Of note, the twice-a-day regimen of RLM appears to be necessary for effective symptom relief; the 10 µg once daily study treatment did not demonstrate significant improvement in symptom relief compared with placebo after 28 days of dosing in Study RM-131-004.

Review of the safety laboratory data collected in RM-131-009 revealed a dose-related increase in HbA1c values. Although the variability in HbA1c response was high across all treatments, the 30 µg BID and 100 µg BID doses demonstrated an increase in HbA1c values that was approximately twice as much as observed for the 10 µg BID dose after 12 weeks of study. Shorter durations of treatment (4 weeks) with 10 µg BID of RLM, as observed in Study RM-131-004, did not demonstrate this increase in HbA1c in diabetic participants.

### 4.4. End of Study Definition

This study will continue until RLM becomes commercially available or the sponsor terminates development.

A participant is considered to have completed the study if he/she has completed a final visit assessment.

Relamorelin

## 5. Study Population

The target population is adult participants with DG who have successfully completed Study RLM-MD-03 or RLM-MD-04. Prospective approval of protocol deviations to enrollment criteria, also known as protocol waivers or exemptions, is not permitted.

### 5.1. Inclusion Criteria

Participants are eligible to be included in the study only if all the following criteria apply:

1. Successful completion of either Study RLM-MD-03 or Study RLM-MD-04 (completed final study visit), and rolling over into Study 3071-305-020 in  $\leq 30$  days; eligible participants who completed these studies prior to administrative initiation of this protocol at their study center, will also be allowed to participate in this continued-access study
2. Ability to provide written IC prior to any study procedures and willingness and ability to comply with study procedures
3. Demonstration of adequate compliance with the study procedures in Study RLM-MD-03 or RLM-MD-04, in the opinion of the investigator

### 5.2. Exclusion Criteria

Participants are excluded from the study if any of the following criteria apply:

1. Participant is planning to receive an investigational drug (other than study intervention) or investigational device at any time during Study 3071-305-020.
2. Participant has an unresolved AE from a lead-in study that, in the investigator's opinion, would limit the participant's ability to participate in the study (see also Section 8).
3. Any other reason that, in the investigator's opinion, would confound proper interpretation of the study or expose a participant to unacceptable risk, including renal, hepatic, or cardiopulmonary disease
4. Females who are pregnant, nursing, or planning a pregnancy during the study

Relamorelin

5. Participant is directly or indirectly involved in the conduct and administration of this study as an investigator, sub-investigator, study coordinator, other study staff member, or employee of Allergan; or the participant is a first-degree family member, significant other, or relative residing with one of the above persons involved directly or indirectly in the study; or the participant is enrolled in this study at another clinical study site.

### **Rationale for Inclusion and Exclusion Criteria**

The inclusion and exclusion criteria are meant to create a population of participants that is well characterized as having DG with symptoms that require chronic treatment.

### **5.3. Lifestyle Considerations**

There are no specific dietary restrictions in the study. It is expected that participants are aware of the importance of maintaining reasonable consistency in treating DM and maintaining healthy lifestyle and dietary restrictions for achieving adequate control of hyperglycemia.

### **5.4. Screen Failures**

Screen failures are defined as participants who consent to participate in the clinical study but are not subsequently entered in the study.

Individuals who do not meet the criteria for participation in this study (screen failures) may not be rescreened.

## **6. Study Intervention**

Study intervention is defined as any investigational intervention(s), marketed product(s), placebo, or medical device(s) intended to be administered to a study participant according to the study protocol.

The only study intervention planned is the daily administration of RLM 10 µg SC BID.

### **6.1. Study Interventions Administered**

Participants are to self-administer open-label study intervention SC BID with the first daily dose being administered within approximately 30 minutes before the morning meal (ie, breakfast at approximately 08:00) and the second daily dose within approximately 30 minutes before the evening meal (ie, dinner at approximately 18:00). If a participant does not eat morning or

Relamorelin

evening meals, study intervention is to be administered during typical meal times (eg, 06:00 to 09:00 and 17:00 to 20:00).

If a participant misses a dose before either the morning or evening meal, he/she is to adjust his/her study intervention administration as follows:

- If within 6 hours of the normal dosing time relative to the morning or evening dose, the participant is to self-administer the dose at that time.
- If more than 6 hours after the normal dosing time relative to the morning or evening dose, the participant is not to self-administer the dose, and should resume normal dosing at the next scheduled time (ie, that evening if the morning dose was missed, or the next morning if the evening dose was missed).

Participants are to rotate injection sites in the abdomen.

Study intervention will be dispensed as pen injectors with prefilled cartridges of RLM. Study intervention details are provided in [Table 6-1](#).

**Table 6-1 Study Intervention Details**

Study Intervention	RLM
Dosage Formulation	Prefilled cartridge in multi-dose pen injector
Unit Dose Strength	10 µg dose
Route of Administration	SC
Dosing Instructions	Administer twice daily
Packaging and Labeling	Study intervention will be provided in a single unit carton. Each carton will be labeled as required per country requirement.
Manufacturer	Baxter (prefilled cartridge) Allergan (assembled pen) Sharp (assembled pen)
Injection Device	Utilize multi-dose pen injector for the administration of the study intervention. Refer to the Relamorelin Pen Investigational Directions for Use for detailed instructions on use of the injection device. Each pen injector is to be used for 28 days.

Approval Date: 12-Feb-2021 17:39:44 (GMT)

## Relamorelin

**6.1.1. Study Supplies**

1. The Allergan-manufactured medical devices (or devices manufactured for Allergan by a third party) provided for use in this study are: (1) prefilled cartridge, and (2) multi-dose pen injector.
2. Instructions for medical device use are provided in the Relamorelin Pen Investigational Directions for Use
3. Medical device incidents, including those resulting from malfunctions of the device, must be detected, documented, and reported by the investigator throughout the study (see Section 8.3.6).
4. Other medical devices (not manufactured by or for Allergan) provided for use in this study may include a glucometer.

**6.2. Preparation/Handling/Storage/Accountability**

1. The investigator or designee must confirm appropriate temperature conditions have been maintained during transit for all study intervention received and any discrepancies are reported and resolved before use of the study intervention.
2. Only participants enrolled in the study may receive study intervention, and only authorized site staff may supply or administer study intervention. All study intervention must be stored in a secure, environmentally controlled, and monitored (manual or automated) area in accordance with the labeled storage conditions with access limited to the investigator and authorized site staff.
3. The investigator, institution, or the head of the medical institution (where applicable) is responsible for study intervention accountability, reconciliation, and record maintenance (ie, receipt, reconciliation, and final disposition records).
4. Further guidance and information for the final disposition of unused study interventions are provided in the Study Reference Manual.
5. Devices that are damaged during shipment or at the site or that malfunction during use must be accounted for and returned. The investigator will promptly notify the sponsor's Clinical Research department of any device malfunction. The Clinical Research or Product Support representative will provide instruction for the return of any faulty device for evaluation.

Relamorelin

### **6.3. Measures to Minimize Bias: Randomization and Blinding**

This is an open-label study. No blinding of assigned study intervention will occur.

### **6.4. Study Intervention Compliance**

Study intervention compliance will be assessed using participant recall during each study visit.

The study centers will keep an accurate drug disposition record that specifies study intervention dispensed to each participant and the date of dispensing.

### **6.5. Concomitant Therapy**

Any medication or vaccine (including over-the-counter or prescription medicines, vitamins, and/or herbal supplements) that the participant is receiving at the time of enrollment or receives during the study must be recorded on the eCRF along with:

- Reason for use
- Dates of administration including start and end dates
- Dosage information including dose and frequency

Prior medications that were ongoing at the end of Studies RLM-MD-03 and RLM-MD-04 will be automatically transferred into the Study 3071-305-020 database.

As much as possible, the dose and frequency of all concomitant medications taken for chronic conditions with the exception of DM are to be held stable during the study. The sponsor is to be contacted if there are any questions regarding concomitant or prior therapy. Diabetic medications will be adjusted as needed to keep glycemic control at a steady level (Section 6.5.2).

